##### **Screening & Enrollment**

Women will be enrolled in Lilongwe, Malawi, a city with a population of 900,000. Participants will complete an interviewer-administered baseline questionnaire to collect socio-demographic data and cervical cancer risk factors. Baseline evaluation will include urine pregnancy testing, HIV rapid finger stick testing, and blood for CD4+ T cell count and HIV-1 RNA testing for HIV-positive women. Urine samples collected for pregnancy testing will also undergo Xpert HPV testing and S5 methylation testing. These urine tests are only for research purposes and results will not influence patient management.

Women will receive simple instructions on how to self-collect a cervicovaginal sample with vaginal brush for hr-HPV testing in the research clinic, using well-validated, field-tested illustrated instructions that are comprehensible to low-literacy women. The self-collection kit will contain a vaginal brush and vial of

sample preservation solution. Participants will then collect this brush, which will be tested onsite using Xpert HPV testing. HPV-negative women will be advised to continue with routine ICC screening per Malawi Cervical Cancer Guidelines. HPV-positive women will complete same-day VIA, using 3-5% acetic acid on the cervix for at least 1 minute, then observing for color changes indicating the presence of a lesion, as described in the WHO IARC Manual. We will also perform same-day VIA on every 10th consecutive woman found to be HPV-negative to assess for possible underscreening with self-HPV testing.

All women who undergo speculum exam will have a provider-collected swab performed, which will be sent for hr-HPV and S5 methylation testing. The results from these tests will be used to help evaluate the validity of urine hr-HPV and S5 testing; they will not be used to influence patient management.

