For all women who undergo VIA, we will determine if a woman is VIA-positive and ablation-eligible using colposcopy with Mobile ODT EVA system. Women who are VIA-positive will undergo colposcopically-directed biopsies of the acetowhite lesion, with at least 2 and up to 4 biopsies taken, as well as an ECC. If the woman is still considered to be ablation-eligible by colposcopy, she will then undergo thermocoagulation. Women who are VIA-negative will also undergo colposcopy, and at least 2 and up to 4 cervical biopsies and ECC if a lesion is seen at colposcopy. Thermocoagulation will also be performed on these women if they are found to have an ablation-eligible lesion on colposcopy. If no lesion is seen on colposcopy, the woman will have cervical pap smear and ECC collected, and no thermocoagulation will be performed. Women who are suspicious for cancer at VIA will undergo colposcopically-directed cervical biopsies. Whenever biopsy is indicated, we will perform at least 2 cervical biopsies on women because previous studies have shown that cervical biopsy is most sensitive when at least 2 biopsies are taken. During colposcopy, images of the cervix may be captured with the EVA system. These images will be stored only in password-protected and de-identified study databases, linked only to the study participant PID. The images will be used for internal quality assurance and may also be shared with the sponsor or other parties for research purposes.

For women to undergo thermocoagulation, we will consider them to be ablation-eligible if the following criteria are met at colposcopy: 1) cervical lesions are not suspicious for ICC; 2) cervical lesions are located entirely on the ectocervix; 3) cervical lesions are no more than 2-3 mm into the endocervical canal; 4) the entire squamocolumnar junction (SCJ) can be visualized; and 5) all visible lesions are deemed appropriate for thermocoagulation by the treating provider. Women with suspected endocervical dysplasia, CIS, or ICC will be referred for treatment at the Kamuzu Central Hospital (KCH), a public tertiary and teaching hospital Colposcopy Clinic on which campus UNC Project-Malawi is situated.

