Number (and %) of treated women who return for Week 24 follow up visit and are found to have resolved versus persistent hr-HPV
Number (and %) of treated women who return for Week 24 follow up visiting that are found to have resolved CIN1
Number (and %) of treated women who return for Week 24 follow up visit that are found to have resolved CIN2+
Number (and %) of treated women who return for Week 24 follow up visit that are found to have persistent CIN1+
Number (and %) of treated women who return for Week 24 follow up visit that are found to have persistent CIN2+
Number (and %) of treated women who return for Week 24 follow up visit that are found to have resolved CIN1
Number (and %) of women referred for further management who have received appropriate management by Week 24

We will also calculate the median time needed to complete the proposed HPV testing, VIA triage, and treatment cascade by recording the times for each of the following steps.

- 1) Time that the participant received the self-HPV collection brush
- 2) Time that the participant returned the self-HPV collection brush
- 3) Time that the HPV test was initiated in the Xpert machine
- 4) Time that the HPV test was completed in the Xpert machine
- 5) Time that the participant received her HPV result
- 6) Time that the participant had her VIA completed (if applicable)
- 7) Time that the participant had her colposcopy completed (if applicable)
- 8) Time that the participant had cervical biopsies or cervical cytology, and ECC completed (if applicable)
- 9) Time that the participant had her thermocoagulation completed (if applicable)

Logistic regression models will be used to assess factors associated with completing the proposed testing and treatment cascade for both HPV-positive and HPV-negative women, such as HIV status, length of time on ART, travel time to

attend in-clinic appointments, knowledge of someone with any cancer, HIV-1 RNA load, and CD4+ T cell count. This objective is largely descriptive and, thus, formal power calculations are not made.

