women who are HPV positive/VIA positive/ablation-eligible, and undertreatment among HPV positive/VIA negative women. All HPV positive women and every 10th consecutive HPV-negative woman will undergo VIA. During VIA, we will determine if a woman is VIA-positive and ablation-eligible. Women who are VIA-positive will undergo colposcopically-directed cervical biopsies and endocervical currettings (ECC). If the woman is still considered to be ablation-eligible by colposcopy, she will then undergo thermocoagulation. Women who are VIA-negative will also undergo colposcopy, but they will only have cervical biopsies and ECC performed if a lesion is seen on colposcopy. Following VIA, we will collect directed cervical biopsies and ECC from VIA positive women prior to thermocoagulation treatment if ablation-eligible by colposcopy, or cervical pap smear and ECC from VIA negative women if no lesion is seen at colposcopy. If a lesion is seen at colposcopy, VIA negative will also undergo colposcopically-directed cervical biopsy and ECC. We hypothesize that <25% of HPV positive/VIA positive women would have been overtreated (no CIN2+, but treated) and that <30% of HPV positive/VIA negative women would have been undertreated (CIN2+, but untreated).

Data analysis for secondary objective I: Overtreatment will be calculated as the proportion of HPV positive/VIA positive/ablation-eligible women who would have been treated with thermocoagulation based on their HPV and VIA findings alone (without colposcopy), but were found to have no CIN2+ on colposcopically-directed cervical biopsy or ECC at Screening/Enrollment. This proportion will represent the women with no lesions or low-grade lesions (CIN1) who would have been unnecessarily treated if we based the decision to perform thermocoagulation on HPV and VIA testing alone.

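### Section 4.3 can be read as letting colposcopy set the VIA result, and nothing fixes that result first, so undertreatment may be understated and overtreatment distorted

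*Combined protocol and SAP*

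**What the plan says.** Section 4.3 (Screening & Enrollment) first describes VIA as an inspection: "HPV-positive women will complete same-day VIA, using 3-5% acetic acid on the cervix for at least 1 minute, then observing for color changes". It then says: "For all women who undergo VIA, we will determine if a woman is VIA-positive and ablation-eligible using colposcopy with Mobile ODT EVA system". The sentences that follow treat colposcopy as a further step. Eligibility is judged again ("If the woman is still considered to be ablation-eligible by colposcopy"), and "Women who are VIA-negative will also undergo colposcopy", with biopsies if a lesion is seen there.

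Section 6.3, Secondary objective I, has a near-twin of the key sentence that does not name colposcopy: "During VIA, we will determine if a woman is VIA-positive and ablation-eligible". It also says: "Women who are VIA-negative will also undergo colposcopy, but they will only have cervical biopsies and ECC performed if a lesion is seen on colposcopy".

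The two performance measures in Section 6.3 rest on the VIA result:

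- Overtreatment is the share of HPV-positive, VIA-positive, ablation-eligible women who would have been treated on HPV and VIA findings without colposcopy, yet have no CIN2+.
- Undertreatment is the share of women with CIN2+ who were neither treated nor referred because HPV, VIA or both were negative.

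Section 6.3 also records separate completion times for VIA and colposcopy. No section says that the VIA result must be entered before colposcopy begins, that a second examiner reads it, or that it may not be revised.

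**The concern.** Both measures ask how HPV testing followed by naked-eye VIA would perform where no colposcope is available. They need a VIA result that colposcopy has not informed. Here every woman who has VIA goes on to colposcopy at the same visit, and one procedural sentence can be taken to mean that the colposcope contributes to the VIA call.

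If a lesion seen only through the colposcope is recorded as VIA-positive, a case that VIA missed becomes one that VIA caught. Undertreatment among women with CIN2+ then falls and apparent VIA sensitivity rises. Overtreatment changes too, because women without CIN2+ can also be relabelled.

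The error would be hard to see later. Under Section 4.3 a woman with a colposcopic lesion has biopsies and ECC, and thermocoagulation if eligible, under either VIA label, so a changed label leaves little trace in her care. Section 1.3 says the results are meant to inform national policy, so an understated miss rate would matter.

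**Working it through.** **Inputs.** Section 6.2 gives 625 women per HIV group; hr-HPV positivity of 50% (HIV-positive) and 20% (HIV-negative); and CIN2/3 in 20% and 10% of those. Section 6.3 gives VIA sensitivity 0.69 (95% CI 0.54-0.81) and specificity 0.87. The carry-over share f, the fraction of VIA-missed cases relabelled VIA-positive after colposcopy, is not in the documents. It is an assumption and is varied below.

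**The plan's own count.** HIV-positive: 0.50 × 625 = 312.5, taken as 313, and 0.20 × 313 = 62.6, taken as 63. HIV-negative: 0.20 × 625 = 125, and 0.10 × 125 = 12.5, taken as 13. The total of 63 + 13 = 76 reproduces Section 6.2. HPV-positive women number 313 + 125 = 438, of whom 438 − 76 = 362 have no CIN2/3.

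**Missed cases without carry-over.** 76 × (1 − 0.69) = 23.6, or 31%. Over the sensitivity interval: 76 × 0.19 = 14.4 (19%) to 76 × 0.46 = 35.0 (46%).

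**With carry-over,** the missed count is 23.6 × (1 − f):

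- f = 5%: 22.4 (29.5%)
- f = 10%: 21.2 (27.9%)
- f = 25%: 17.7 (23%)
- f = 50%: 11.8 (16%)

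Crossing 30% on this denominator takes f = 1 − 0.30/0.31 = 3.2%, which is less than one woman of the 23.6.

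**On the other denominator.** Section 6.3 states its 30% hypothesis as a share of HPV-positive/VIA-negative women. VIA-negative women without CIN2/3 number 362 × 0.87 = 314.9. Without carry-over: 23.6 / (23.6 + 314.9) = 7%. At f = 25%: 17.7 / (17.7 + 314.9) = 5%. If 10% of true-negative VIA calls were also relabelled (a second assumption), the non-cases fall to 283.4 and the figure at f = 25% is 17.7 / 301.1 = 5.9%. On this denominator the fall therefore depends on cases being relabelled more often than non-cases.

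**Overtreatment,** taking all VIA-positive women as ablation-eligible. False positives: 362 × 0.13 = 47.1. True positives: 76 × 0.69 = 52.4.

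- No carry-over: 47.1 / 99.5 = 47%.
- f = 25%, cases only: 47.1 / (47.1 + 58.3) = 45%.
- f = 25% and 10% of true negatives relabelled: 78.6 / (78.6 + 58.3) = 57%.

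**Completion outcomes.** Outcome (a), VIA on the same day among HPV-positive women, does not use the VIA result and is the same at every f. Outcome (b) includes colposcopic eligibility by definition, so only its VIA-positive component can change.

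**The case against.** The strongest reply is that the key sentence is ambiguous and that the rest of the document points the other way. Sections 1.1, 1.3, 2.1, 4.1, 6.1 and 6.3 attach colposcopy to ablation-eligibility. Section 5.1 gives VIA and colposcopy separate rows, and Section 6.3 times them separately and in that order. The text after the key sentence provides for a VIA-negative woman with a colposcopic lesion. This stands. A reader might infer that the protocol does define VIA by colposcopy, so that no visible lesion could ever count as missed; the documents do not support that.

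Three further points also stand:

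- Undertreatment includes HPV-negative misses, and CIN2+ found only on ECC with no visible lesion. Carry-over at colposcopy cannot relabel either of these.
- Section 6.3 itself cautions that the 0.69 sensitivity comes from primary screening, not from triage of HPV-positive women.
- Against the VIA-negative denominator, the result is far below 30% with or without carry-over.

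The reply does not supply a safeguard. Separate rows and separate completion times show what was intended and allow the order of examinations to be checked. They do not show when the VIA result was entered or whether it was later changed. Section 6.4 has forms entered in real time and reviewed within 24 hours, but nothing there fixes one field before the next examination starts.

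**Conclusion.** The point holds as a risk that the plan leaves open. Sections 4.3 and 6.3 describe the determination of VIA status differently, and nothing keeps that result independent of the colposcopy that follows. Undertreatment among women with CIN2+ may be understated: 31% expected without carry-over, and 29.5% to 16% for assumed carry-over of 5% to 50%. These figures use CIN2/3 in HPV-positive women as a stand-in for CIN2+, and they rest on the borrowed sensitivity. The true carry-over share is unknown and may be zero.

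A reader might also infer that the completion results are compromised. They are not in general: outcome (a) is untouched, and extra women in the denominator of (b) would bias it only if their same-day treatment rate differed, for which the documents give no reason. Nor can one say that the strategy would look too favourable overall, since overtreatment moves from 47% to 45% or to 57% depending on who is relabelled.

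The exposure is mainly to Secondary objective I, which the plan calls largely descriptive. The change is still worth making before data collection, because a naked-eye result not captured at the visit may not be recoverable.

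**What to change.** 1. Reconcile Sections 4.3 and 6.3 on how VIA status and ablation-eligibility are each determined, and at which step.
2. Require the naked-eye VIA result and the VIA-stage eligibility assessment to be entered, timed and locked in the ODK form before the colposcope or EVA system is used. VIA-stage eligibility is needed because overtreatment is defined without colposcopy.
3. Hold colposcopy findings, including eligibility at colposcopy, in separate fields.
4. Base the undertreatment and overtreatment analyses on the locked VIA-stage record.
5. While editing, state one denominator for undertreatment: Section 6.3 uses women with CIN2+ in the definition and HPV-positive/VIA-negative women in the hypothesis.

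Steps 1 to 4 cost a few sentences of text, one form rule and a small amount of extra entry time per examination. Section 6.4 already has staff entering data on tablets during visits. The documents do not say whether the form can lock a field, so this should be confirmed. Recording the result first changes no woman's care.

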#### **Week 4**

All women who had cervical biopsies or cervical pap smear, and ECC done at Screening/Enrollment will return for histology and/or cytology results at Week 4. HPV-positive/VIA-negative women without CIN or ICC on histology and those with normal cytology will be advised to continue with routine ICC screening per guidelines. Women who underwent thermocoagulation will be evaluated for interval medical history or post-treatment adverse events during this visit. HPV-positive/VIA-negative women with CIN2+ on ECC or abnormal cytology on cervical pap smear will be referred to KCH Colposcopy Clinic for further management.

HPV-positive/VIA-positive women who had CIN detected at baseline cervical biopsy, and underwent thermocoagulation will be followed up at Week 24 post-treatment. Women who had CIN and visible cervical lesion that was not ablation-eligible by colposcopy or had ICC will be referred to KCH Colposcopy clinic for further management.

Women who are HPV-positive may be enrolled in and consented for IDIs at their Week 4 visit. These interviews will be conducted similarly to those done at the Screening/Enrollment visit but they will also cover women's experiences sharing their screening results with others and abstaining from sex for the recommended interval after biopsy/thermocoagulation.

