### **Week 28**

All women who had cervical biopsy or cervical pap smear, and ECC done at Week 24 will be asked to return at this visit for histology and/or cytology results and any necessary follow-up referrals to KCH Colposcopy Clinic.

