### **4.4 Expected Risks**

The following are possible risks due to participant enrollment into our study:

**4.4.1 Sample collection:** Risks to study participant include the physical risks from blood draw, vaginal and cervical sample collection, cervical biopsies, and ECC. Participants can experience pain, bleeding, and sometimes infection, and damage to tissue at the site of the sample collection. However, all these sample collections are done as part of routine clinical evaluations when indicated in women of reproductive age and are considered to be minimal risks.

**4.4.2 Treatment with thermocoagulation:** Risks include pain, infection, and damage to tissue at the site of treatment application, i.e., the cervix. These risks are considered minimal. Thermocoagulation is not associated with future fertility compromise or adverse pregnancy outcomes in future pregnancies.

Thermocoagulation is used for treating VIA-positive women in some cervical cancer screening programs including Malawi.

4.4.3 Psychological risks might arise if a participant's peer or partner finds out about her study participation and does not approve of it. In addition, participants might also have some embarrassment or discomfort providing urine samples; or answering sensitive questions during the survey, but they can opt not to answer such questions. Women who participate in the IDIs may have further risk of embarrassment or discomfort about answering sensitive questions, but they can opt not to answer and they will be assured that doing so will not affect their ability to remain in the study or receive necessary health care.

To address these risks, informed consent forms will be administered in Chichewa, the local national language that participants and study staff are fluent in, and only participants who demonstrate comprehension through a standard comprehension checklist will be enrolled in the study after providing written informed consent. During the informed consent process, participants will be counseled about the potential risks, benefits and side effects of study procedures. Only study staff trained in the Biomedical Research and Good Clinical Practices will be involved in the study. Study procedures, risks, and benefits will be discussed with study participants, and study staff will answer all questions prior to obtaining consent. Each woman will be fully informed regarding the reasonably foreseeable impact of the research on her circumstances.

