## 5.0 TIME AND EVENTS TABLE

### 5.1 Schedule of study procedures

Study Visit	Screening & Enrollment	Week 4	Week 24	Week 28
Women who will attend the study visit	All women	Women who had cervical biopsy or cervical pap smear, and ECC done at Screening & Enrollment	Women who had CIN1+ at Screening & Enrollment and underwent thermocoagulation	Women who attended the Week 24 Visit
Evaluations				
Informed consent	X			
Baseline survey	X			
Urine pregnancy testing	X	X	X	
HIV-1 Rapid Test (2 kits)	X			
HIV-1 Confirmatory Test 	X			
CD4+ T cell count 	X			
HIV-1 RNA (plasma) 	X			
Self-collected vaginal brush	X			
hr-HPV testing of self-collected samples	X		X	
hr-HPV and S5 methylation testing of urine sample	X			
Provider-collected cervical brush	X 		X	
hr-HPV testing of provider-collected cervical sample	X 			
S5 methylation testing of provider-collected cervical sample	X 			
VIA 	X			
Colposcopy and cervical biopsy or cervical pap smear, and ECC 	X		X	
Thermocoagulation 	X			
Thermocoagulation-related adverse events evaluation		X		
Provide results and any referrals		X		X
Follow-up questionnaire 		X		
Enroll for IDIs	X	X		

For those with discordant HIV rapid tests.

For HIV-positive participants only

For all hr-HPV+ and for every 10th woman who is hr-HPV-.

Cervical biopsy and ECC if lesion seen at colposcopy; Cervical pap smear and ECC if no lesion seen at colposcopy

For women with ablation-eligible cervical lesion at colposcopy.

For follow-up of cervical histology and/or cytology results from Screening/Enrollment and to assess for any change in history or adverse events from thermocoagulation (if thermocoagulation was performed).

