#### 7.3.3.2. Procedures for Reporting Incidents

1. All study staff are responsible for reporting known or suspected adverse events (AE), protocol deviations, or UPIRSO immediately (the same day of the incident or discovery of the incident) to the Study Coordinator.
2. If an incident involves harm or injury to a person, the next step is to eliminate immediate hazard to the subject(s) or others. Immediate corrections do not require IRB approval prior to initiation, but should be described in the Incident Report.
3. Routine reporting of AE: all AE will be source documented. The following will be reported on a case report form:
  - a) All genital AE regardless of grade and severity,
  - b) All AEs with grade  $\geq 3$ .
4. The Study Coordinator must determine if the incident requires prompt reporting to the IRBs. If so, the Study Coordinator must report the incident immediately (the same day of the incident or discovery of the incident) to the PI so that he can notify the IRBs within 7 calendar days of notification.
5. The following incidents require prompt reporting to the IRBs:

- a. AEs that are:
  - Unexpected,
  - Related or Possibly Related to participation in the research and are grade  $\geq 3$ , and
  - Serious or suggest that there are new or increased risk(s) to subjects.
- b. Interim analysis, data and safety monitoring report, findings from other studies, findings from animal or in-vitro testing, or other finding(s) that indicate: (1) there are new or increased risks to subjects or others, or (2) subjects are less likely to receive any direct benefits from the research.
- c. Protocol deviations that harmed subject(s) or others or placed subject(s) or others at increased risk of harm.
- d. Protocol deviations that are made to eliminate an immediate hazard to a subject without IRB approval.
- e. Intentional or unintentional failure to follow applicable federal human subject protection regulations, the requirements or determinations of the IRB, the IRB-approved study protocol, or University policies when that failure adversely affects the rights or welfare of participants, such as:
  - Conducting human subjects research without an IRB-approved protocol or exemption
  - Starting research prior to meeting the conditions required by the IRB and receiving an IRB notification of approval, or conducting research during a lapse in approval
  - Failure to obtain informed consent

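### Scheduled adverse-event questioning covers thermocoagulation but not biopsy and ECC: women who were not ablated are not explicitly asked at Week 4, and nobody is asked at Week 28

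*Combined protocol and SAP*

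**What the plan says.** **Risks.** Section 4.4.1 lists "the physical risks from blood draw, vaginal and cervical sample collection, cervical biopsies, and ECC", and continues: "Participants can experience pain, bleeding, and sometimes infection, and damage to tissue at the site of the sample collection".

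**Recording.** Section 7.3.3.2 requires staff to report known or suspected AEs the same day. It sends to the case report form "All genital AE regardless of grade and severity", plus all AEs of grade 3 or higher. Neither rule depends on the procedure received.

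**Week 4.** Attendance is wide: "All women who had cervical biopsies or cervical pap smear, and ECC done at Screening/Enrollment will return for histology and/or cytology results at Week 4". The AE evaluation is narrower: "Women who underwent thermocoagulation will be evaluated for interval medical history or post-treatment adverse events during this visit". The only AE row in the section 5.1 schedule is "Thermocoagulation-related adverse events evaluation", with one mark, under Week 4. Footnote 6, on the Week 4 follow-up questionnaire, mentions changes in history and AEs from thermocoagulation where it was done.

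**Week 24.** The text in section 4.3 also provides for an evaluation of interval history and post-treatment AEs. The schedule row has no mark there. At this visit ECC is repeated, with 2 to 4 biopsies if a lesion is seen and a Pap smear if not.

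**Week 28.** Women "return at this visit for histology and/or cytology results and any necessary follow-up referrals to KCH Colposcopy Clinic". No AE evaluation is listed in the text or the schedule.

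**The concern.** The plan names harms from biopsy and ECC and wants all genital AEs recorded, but schedules questions only about the treatment. Two groups fall outside that questioning:

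- women who had biopsy plus ECC, or Pap smear plus ECC, without thermocoagulation, although they attend at Week 4;
- all women who had ECC (and perhaps biopsies) again at Week 24, although they attend at Week 28.

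For these exposures the plan depends on events being volunteered or noticed. Ascertainment is then active in ablated women and passive in the rest, so genital AE counts would not be comparable between them. Biopsy and ECC events would probably be under-counted. Bleeding or infection in a woman already in the clinic could go unasked. Section 7.3.3.1 requires each AE to be assessed for attribution. In ablated women biopsy, ECC and thermocoagulation fall on the same day, so that judgement would have no equally questioned group to set beside it.

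**Working it through.** **1. The plan's own counts (section 6.2).**
- HPV-positive: 625 × 0.50 = 312.5 (313) HIV-positive women; 625 × 0.20 = 125 HIV-negative women.
- CIN2/3: 313 × 0.20 = 62.6 (63); 125 × 0.10 = 12.5 (13); total 76.
- After 5% loss: 76 × 0.95 = 72.2 (72); 63 × 0.95 = 59.9 (60).

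These reproduce the stated 313, 125, 63, 13, 76, 72 and 60.

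**2. Women examined at baseline.** All HPV-positive women and every tenth HPV-negative woman are examined.
- HPV-positive: 313 + 125 = 438.
- HPV-negative: 1,250 − 438 = 812; one tenth is about 81.
- Total: 438 + 81 = 519.

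Nearly all have ECC, because section 4.3 collects it whether or not a lesion is seen. Women suspicious for cancer are listed for biopsies only, so 519 is a slight upper bound at these prevalences.

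**3. Share not ablated.** The documents do not give the number ablated. Three approximations follow.

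(a) Assume 100 to 200 ablated: 519 − 200 = 319 (61%) to 519 − 100 = 419 (81%).

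(b) Take VIA-positive women as a stand-in for those ablated, with the pooled VIA accuracy cited in section 6.3 and no CIN2/3 among the 81 HPV-negative women. The number is 76 × sens + (438 − 76) × (1 − spec) + 81 × (1 − spec).

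| Sensitivity | Specificity | VIA-positive | Not ablated, of 519 |
|---|---|---|---|
| 0.69 | 0.87 | 52.4 + 47.1 + 10.5 = 110.0 | 409 (79%) |
| 0.54 | 0.92 | 41.0 + 29.0 + 6.5 = 76.5 | 443 (85%) |
| 0.81 | 0.79 | 61.6 + 76.0 + 17.0 = 154.6 | 364 (70%) |
| 1.00 | 0.79 | 76.0 + 76.0 + 17.0 = 169.0 | 350 (67%) |

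Rows two and three use the cited confidence limits. Row four goes beyond them, as a stress test.

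(c) Treat all 76 CIN2/3 cases, with overtreatment at the hypothesised ceiling of 25%: 76 / 0.75 = 101 ablated, 418 (80%) not.

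**4. When 'most' would fail.** Half of 519 is 259.5, so about 260 would have to be ablated. With all 76 CIN2/3 cases treated, that needs overtreatment of 1 − 76/259.5 = 71%.

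**5. Repeat procedures.** If the 76 CIN2/3 cases are treated, about 72 return at Week 24, plus treated women with CIN1. All are due a repeat ECC. The Week 24 evaluation takes place at that same visit, so it cannot capture events that follow the ECC. Week 28 is the only later scheduled visit.

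**The case against.** A reader might infer that AEs are evaluated only at Week 4, that everyone else has no AE evaluation, or that biopsy events will automatically be charged to thermocoagulation. The documents support none of these. The Week 24 text also provides an evaluation. Section 7.3.3.2 captures every genital AE that becomes known, whatever the procedure. Section 7.3.3.1 requires relatedness and attribution to be judged for each AE.

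Footnote 6 can also be read as asking all Week 4 attendees about any change in history, with only the thermocoagulation item conditional. The questionnaire is not in the documents, so what women who were not ablated are actually asked cannot be known. The Week 4 text reads more narrowly, and the two need reconciling.

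The sponsor could add that the focus is deliberate: sections 4.4 and 7.4 describe sample collection, biopsy and ECC as routine when indicated. That is a fair reason to give thermocoagulation priority. It is weaker here because the study itself creates some of the exposure, through the sampled HPV-negative women and through ECC where no lesion is seen.

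Two further points stand. No objective or analysis visible in the documents estimates AE rates, so no planned primary or secondary result changes. And a tabulation by procedure would not isolate the effect of ablation, because women are ablated according to lesion and eligibility. What the objection does not supply is a scheduled question: recording rules act only on events already known or suspected.

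**Conclusion.** The concern holds as a gap in scheduled, active ascertainment, not as an absence of AE capture. At Week 4 there is no explicit AE questioning of women who had biopsy or ECC without thermocoagulation, subject to the ambiguity in footnote 6. At Week 28 there is none for anyone, after a second round of procedures. Spontaneous reports are captured throughout.

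Roughly 60% to 85% of about 519 examined women fall in the passive group at baseline. This rests on the plan's prevalence inputs and on an assumed number ablated. The VIA accuracy figures were for primary screening, as section 6.3 says, and the stand-in omits VIA-negative women treated for a lesion seen at colposcopy. Section 6.3 also mentions a high VIA false-positive rate in a pilot, without a figure. Each of the last two could lower the share, but 'most' survives unless about 260 women are ablated. These are counts of women, not of missed events; the documents give no event rate for biopsy or ECC.

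The change is worth making, because it improves safety detection and evens out ascertainment at visits that already exist.

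**What to change.** - In section 5.1, rename the AE row *Procedure-related adverse events evaluation (biopsy, ECC, thermocoagulation)* and mark it for all Week 4 and all Week 28 attendees.
- Show in the same row the Week 24 evaluation that section 4.3 already describes.
- Reword the Week 4 text and footnote 6 so that both put the same AE questions to every attendee, and add the evaluation to the Week 28 text.
- In section 6.3, add a descriptive table of genital AEs by procedures received (Pap smear plus ECC; biopsy plus ECC; biopsy, ECC and thermocoagulation). State that the groups are not randomised and do not isolate the effect of ablation.

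The cost is a few minutes of questions at existing visits, small form changes, and a protocol amendment approved by both the UNC IRB and the Malawi NHSRC (section 7.5). Sample size, treatment and visit schedule do not change.
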